ALT	Alanine transaminase
AM	Arithmetic mean
ATS	American Thoracic Society
AUC(0-last)	Area under the curve (from zero to last)
AUC(0-∞)	Area under the curve (from zero to infinity)
AxMP	Auxiliary medicinal product
BMI	Body mass index
Cmax	Maximum plasma concentration
CA	Competent authority
CFC	Chlorofluorocarbon
CFR	Code of Federal Regulations
CI	Confidence intervals
CIOMS	Council for International Organizations of Medical Sciences
CONSORT	Consolidated Standards of Reporting Trials
COVID-19	Coronavirus disease 2019
CPK	Creatine phosphokinase
CRF	Case report form
CSR	Clinical study report
CVw	Within-subject coefficient of variation
eCRF	Electronic case report form
ECG	Electrocardiogram
EMA	European Medicines Agency
ERS	European Respiratory Society
FDA	Food and Drug Administration, United States of America
FSFV	First subject first visit
FSH	Follicle stimulating hormone
GCP	Good Clinical Practice
GM	Geometric mean
GMR	Geometric mean ratio
GWP	Global warming potential
HBsAg	Hepatitis B surface antigen

Abbreviation	Definition
hCG	Human Chorionic Gonadotropin
HCV	Hepatitis C virus
HFA	Hydrofluoroalkane
HFA-134a	1,1,1,2-tetrafluoroethane
HFA-152a	1,1-difluoroethane
HIV	Human immunodeficiency virus
HR	Heart rate
HRT	Hormonal Replacement Therapy
ICE	Intercurrent event
ICF	Informed consent form
ICH	International Council for Harmonization
ICMJE	International Committee of Medical Journal Editors
ICSR	Individual case safety reports
IDSL	Integrated Data Standards Library
IEC	Independent Ethics Committee
IFU	Instructions for use
IgM	Immunoglobulin M
IMP	Investigational Medicinal Product
INR	International Normalized Ratio
IRB	Institutional Review Board
LDH	Lactate Dehydrogenase
LLOQ	Lower Limit of Quantification
LSLV	Last Subject Last Visit
MDI	Metered Dose Inhaler
MHR	Maximum Heart Rate
MedDRA	Medical Dictionary for Regulatory Activities
MSDS	Material Safety Data Sheet
NIMP	Non-investigational medicinal product
PCR	Polymerase Chain Reaction
PD	Pharmacodynamic(s)
PK	Pharmacokinetic(s)
PR	Pulse Rate
QTc	Corrected QT interval
QTcF	QT interval corrected using Fridericia's formula
QTL	Quality tolerance limit
RR	Respiratory Rate
RSABE	Reference-scaled average bioequivalence

Abbreviation	Definition
SD	Standard Deviation
SADE	Serious adverse device effect
SAE	Serious adverse event
SARS-CoV-2	Severe acute respiratory syndrome-corona virus type 2
SmPC	Summary of product characteristics
SoA	Schedule of activities
Tmax	Time to reach maximum plasma concentration
TEAE	Treatment-emergent adverse event
THC	Tetrahydrocannabinol
ULN	Upper limit of normal
USADE	Unanticipated serious adverse device effect
WHO	World Health Organization
WOCBP	Woman of childbearing potential
WONCBP	Woman of nonchildbearing potential

Term	Definition
Adverse Drug Reaction	
An adverse event where a causal relationship between a medicinal product and the adverse event is at least a reasonable possibility, i.e., the relationship cannot be ruled out.
 
a. In the context of a clinical trial, an ADR can be serious or non-serious. Serious ADRs may be subject to expedited reporting if they are considered unexpected (see SUSAR definition).
 
b. For marketed products, ADRs are subject to expedited reporting within the country where they are authorized

Auxiliary Medicinal Product (AxMP)	
Medicinal products used in the context of a clinical trial but not as investigational medicinal products, such as medicinal products used for background treatment, challenge agents, rescue medication, or used to assess endpoints in a clinical trial. Auxiliary medicinal products should not include concomitant medications, that is medications unrelated to the clinical trial and not relevant for the design of the clinical trial.
 
a. Authorized AxMP
 
Medicinal product authorized in accordance with Regulation (EC) No 726/2004, or in any Member State concerned in accordance with Directive 2001/83/EC,

Term	Definition
b. Unauthorized AxMP	
irrespective of changes to the labeling of the medicinal product.
 
1. Safety reporting with regard to auxiliary medicinal products shall be made in accordance with Chapter 3 of Title IX of Directive 2001/83/EC.
 
a. Medicinal product not authorized in accordance with Regulation (EC) No 726/2004.
 
1. Safety reporting for unauthorized auxiliary medicinal products will follow the same processes and procedures as SUSAR safety reporting.

Background treatment	
Type of medicinal product administered to each of the clinical trial participant, regardless of randomization group, to treat the indication that is the object of the study. Background treatment is generally considered to be the current standard care for the particular indication. In these trials, the IMP is given in addition to the background treatment and safety efficacy are assessed. The protocol may require that the IMP plus the background treatment is compared with an active comparator or with placebo plus background treatment.

Blinding	
A procedure in which 1 or more parties to the study are kept unaware of the intervention assignment in order to reduce the risk of biased study outcomes. The level of blinding is maintained throughout the conduct of the study, and only when the data are cleaned to an acceptable level of quality will appropriate personnel be unblinded or when required in case of a SAE.
 
In an open-label study, no blind is used. Both the investigator and the participant know the identity of the intervention assigned.

Certified copy	
A copy (irrespective of the type of media used) of the original record that has been verified (i.e., by a dated signature or by generation through a validated process) to have the same information, including data that describe the context, content, and structure, as the original.

Challenge agents	
A product given to trial participants to produce a physiological response that is necessary before the pharmacological action of the IMP can be assessed.

Combination product	
Combination product comprises any combination of

Term	Definition
	
 • drug • device • biological product 
Each drug, device and biological product included in a combination product is a constituent part.

Comparator	
Any product used as a reference (including placebo, marketed product, GSK or non-GSK) for an investigational product being tested in a clinical trial. This is any product that is being used to assess the safety, efficacy, or other measurable value against the test product (IMP).

Co-administered (concomitant) products	
A product given to clinical trial participants as required in the protocol as part of their standard care for a condition which is not the indication for which the IMP is being tested and is therefore not part of the objective of the study.

Eligible	
Qualified for enrollment into the study based upon strict adherence to inclusion/exclusion criteria.

Essential documents	
Documents which individually and collectively permit evaluation of the conduct of a study and the quality of the data produced

Intervention Number	
A number identifying an intervention to a participant, according to intervention allocation.

Investigational product	
A pharmaceutical form of an active substance or placebo being tested or used as a reference in a clinical trial, including products already with a marketing authorization but used or assembled (formulated or packaged) in a way different from the authorized form, or when used for an unauthorized indication, or when used to gain further information about the authorized form.

Investigator	
A person responsible for the conduct of the clinical study at a study site. If a study is conducted by a team of individuals at a study site, the investigator is the responsible leader of the team and may be called the principal investigator.
 
The investigator can delegate study-related duties and functions conducted at the study site to qualified

Term	Definition
	individual or party to perform those study-related duties and functions.
Legally acceptable representative	
An individual, judicial or other body authorized under applicable law to consent on behalf of a prospective participant to the participant's participation in the clinical study.
 
The terms legal representative or legally authorized representative are used in some settings.

Medicinal products used to assess endpoints	A product given to the participant in a Clinical Trial as a tool to assess a relevant clinical trial endpoint; it is not being tested or used as a reference in the clinical trial.
Participant Number	A unique identification number assigned to each participant who consents to participate in the study.
Participant	
Term used throughout the protocol to denote an individual who has been contacted to participate or who participates in the clinical study as a recipient of the study intervention.
 
Synonym: subject

Placebo	An inactive substance or treatment that looks the same as, and is given in the same way as, an active drug or intervention/treatment being studied.
Randomization	Process of random attribution of intervention to participants to reduce selection bias.
Rescue medication	Medicines identified in the protocol as those that may be administered to the participants when the efficacy of the IMP is not satisfactory, or the effect of the IMP is too great and is likely to cause a hazard to the patient, or to manage an emergency situation.
Source data	All information in original records and certified copies of original records of clinical findings, observations, or other activities in a clinical study necessary for the reconstruction and evaluation of the study. Source data are contained in source documents (original records or certified copies).
Standard of Care	Medicine(s) for a specific indication, or a component of the standard care for a particular medical indication,

Term	Definition
	
based on national and/or international consensus; there is no regulatory significance to this term.
 
1. Products/regimens considered standard of care may differ country to country, depending on consensus in individual countries

Study intervention	
Term used throughout the clinical study to denote a set of investigational product(s) or marketed product(s) or placebo intended to be administered to a participant.
 
Note: “Study intervention” and “study treatment” are used interchangeably unless otherwise specified.

Study completion date	
The date on which the last participant in a clinical study was examined or received an intervention/treatment to collect final data for the primary outcome measures, secondary outcome measures, and AEs (that is, the last participant’s last visit or LSV).

Study monitor	
An individual assigned by the sponsor and responsible for assuring proper conduct of clinical studies at 1 or more investigational sites.

SUSAR	
Suspected Unexpected Serious Adverse Reaction; in a clinical trial, a serious adverse reaction that is considered unexpected, i.e., the nature or severity of which is not consistent with the reference safety information (e.g., Investigator’s Brochure for an unapproved investigational medicinal product). All adverse drug reactions (ADRs) that are both serious and unexpected are subject to expedited reporting

1. PROTOCOL SUMMARY

1.1. Synopsis

Protocol Title:

A Phase 1, randomized, open-label, single dose, 2-treatment arm (200 µg and 800 µg), 4-way cross-over study in healthy participants aged 18 to 55 to compare the pharmacokinetics of salbutamol administered via metered dose inhalers containing propellants HFA-152a (test) and HFA-134a (reference).

Brief Title:

A study to compare the pharmacokinetics of salbutamol administered via metered dose inhalers containing propellants HFA-152a (test) or HFA-134a (reference) in healthy participants aged 18 to 55 inclusive.

Rationale:

In current MDIs, micronized particles are suspended in propellant HFA-134a which has a significant global warming potential. GSK is seeking to develop a low carbon footprint alternative propellant, HFA-152a which will address global climate change. Refer to Section 2.1 for further information.

Objectives, Endpoints, and Estimands:

The primary objective of this study is to characterize the PK of single doses of salbutamol in healthy participants delivered via an MDI containing propellant HFA-152a (test), and to compare with an MDI containing propellant HFA-134a (reference) in Cohort 1 with 200 µg and Cohort 2 with 800 µg. The primary PK endpoints are AUC(0-30min), AUC(0-∞) and Cmax. Refer to Section 3 for further information.

Overall Design:

This a randomized, open-label, single dose, 2-sequence, 2-treatment arm, 4-way cross-over (2x2x4) single-center study in healthy participants aged 18 to 55 years. Salbutamol will be administered as either a 200 µg or 800 µg dose, given as 2 or 8 actuations respectively at 20 second intervals, each delivering 100 µg as the ex-valve dose of HFA-152a or HFA-134a.

[figure not shown]
Number of Participants:

The study has planned to enroll a total of 60 participants; 30 participants will be enrolled on to Cohort 1 (200 µg) and 30 participants will be enrolled on to Cohort 2 (800 µg). Within each cohort, 15 participants will be randomized to 1 of the 2 treatment sequences (TRRT and RTTR).

Data Monitoring/Other Committee: Refer to Section 10.1.6.

1.2. Schema

[figure not shown]
Figure 1 Study Design Overview (Cohort 1 – 200 µg dose)

Treatment T: Salbutamol HFA-152a (Test)
Treatment R: Salbutamol HFA-134a (Reference)

Note. Participants enrolled on to cohort 1 (200 µg) will be randomized to 1 of 2 treatment sequences.

Figure 2 Study Design Overview (Cohort 2 – 800 µg dose)

Treatment T: Salbutamol HFA-152a (Test)
Treatment R: Salbutamol HFA-134a (Reference)

Note. Participants enrolled on to cohort 2 (800 µg) will be randomized to 1 of 2 treatment sequences.

1.3. Schedule of activities (SoA)

Table 1 Schedule of Activities

Procedure	Screening		Intervention period (days) ^a										Discharge or early discontinuation	Follow up ^b	
Timepoints	-28 to -1	-1	1 (pre-dose)	1	2	3	4	5	6	7	8	9	10	11	12 to 18
Confinement		X	X	X	X	X	X	X	X	X	X	X	X	X	
Admission		X													
Discharge														X	
Informed consent	X														
Inclusion and exclusion criteria	X	X	X												
Spirometry	X														
Demography	X														
Physical examination ^c	X													X	
Body weight	X														
Height and BMI calculation	X														
Timepoints	-28 to -1	-1	1 (pre-dose)	1	2	3	4	5	6	7	8	9	10	11	12 to 18
Medical history (includes substance usage)	X	X													
Pregnancy test (females only) ^d	X	X												X	

CONFIDENTIAL

219728
Protocol Amendment 1 Final

Procedure	Screening		Intervention period (days) ^a										Discharge or early discontinuation	Follow up ^b	
FSH and estradiol (females only)	X														
Serology (HBsAg, anti-HCV, anti-HIV 1 and 2)	X														
SARS-CoV-2 PCR test ^e		X													
Cotinine, drug, and alcohol screen	X	X													
Clinical laboratory assessments ^f	X	X											X		
Blood sampling for serum potassium (PD) and glucose (safety) ^g			X	X		X		X			X				
Vital signs ^h	X	X	X	X		X		X			X		X		
Timepoints	-28 to -1	-1	1 (pre-dose)	1	2	3	4	5	6	7	8	9	10	11	12 to 18
12-lead ECG ⁱ	X	X	X	X		X		X			X		X		
MDI training ^j		X	X			X		X			X				
Randomization			X												
Administration of study intervention ^k				X		X		X			X				
Blood sampling for PK ^l			X	X	X	X	X	X	X	X	X		X		
AE review ^m				X	X	X	X	X	X	X	X	X	X	X	X
SAE review ^m	X	X	X	X	X	X	X	X	X	X	X	X	X	X	X
Concomitant medication review	X	X	X	X	X	X	X	X	X	X	X	X	X	X	X

a. Intervention period days: Participants will be in the clinic for 1 period, from Day-1 until Day 11 (approximately 24 hours after the last dose on Day 10).

- b. **Follow-up:** The follow-up period is from Day 12 to Day 18. The minimum follow-up procedures that should be conducted are outlined in the follow-up column. However, further follow-up procedures can be conducted at the discretion of the investigator. **Note.** The final follow-up will be conducted via a telephone call. However, it will be at the discretion of the PI whether a follow-up visit would be required i.e., if further investigation is needed.
- c. **Physical examination:** Complete physical examinations will be conducted at screening. Symptom driven physical examinations are conducted at discharge/early withdrawal and may be conducted at any other time, per investigator discretion.
- d. **Pregnancy testing:** Female participants will be required to take a serum pregnancy test (Day-1, Screening and Discharge/Early Withdrawal).
- e. **SARS-CoV-2 PCR testing:** Sampling of nasal and throat mucosal cells for PCR testing for SARS-CoV-2 may be performed at the discretion of the site based on local guidelines.
- f. **Clinical laboratory assessments:** Including clinical chemistry [includes liver chemistries], hematology, and urinalysis will be conducted at screening, on Day-1 (admission), and at discharge.
- g. **Blood sampling for serum potassium (PD) and glucose (safety):** On each dosing day (Day 1, 4, 7 and 10), blood samples will be taken predose at: 15 and 30 minutes and 1, 1.5, 2 and 4 hours postdose.
- h. **Vital signs:** Systolic and diastolic blood pressure, and PR) vital signs will be recorded at screening, admission, on each dosing day (Day 1, 4, 7 and 10) at predose and at the following time points postdose: 15, 30 minutes, 1, 2, 4 hours and at discharge. Assessed after a minimum of 5 minutes of the participant resting in the supine position with a completely automated device.
- i. **12-lead ECG:** 12-lead ECG will be recorded at screening, admission, on each dosing day (Day 1, 4, 7 and 10) at predose and at: 30 minutes postdose and at discharge. As the ECG parameters QTc and HR will be PD parameters, ECG will be measured in triplicate at predose on Days 1, 4, 7 and 10. The 3 predose measures will be recorded in the eCRF and will be averaged for QTc interval and HR to derive 1 baseline value which will be recorded in the eCRF. Each individual capture of the triplicate 12-lead ECG set should be obtained as closely as possible in succession, but no more than 5 minutes apart from first to third ECG. Postdose 12-lead ECG measurements will be single measurements on all dosing days. Discharge or early discontinuation 12-lead ECG measurements will be single measurements. **Note.** if an ECG meets potential stopping criteria, then the ECG measurement should be repeated in triplicate, with the averaged QT and QTcF used to determine stopping.
- j. **MDI training:** Participants will be trained using a placebo HFA-134a propellant via an MDI on Day-1 and prior to dosing on each dosing day (Day 1, 4, 7 and 10). On dosing days, participants should review the instructions use the placebo MDI. The investigator or delegate are to observe the participant performing a single puff using the placebo MDI and provide feedback as necessary until proper technique is observed before conducting the full dose using the investigational inhaler. Additional training using the placebo MDI (e.g., on Day 3) may be performed at the discretion of the site.
- k. **Administration of study intervention:** 8 inhalations of 100 µg (800 µg total) of study intervention or 2 inhalations of 100 µg (200 µg total) of study intervention, with the inhalations administered at 20-second intervals.
- l. **PK blood sampling:** on each dosing day (Day 1, 4, 7 and 10) PK blood samples will be taken at predose, at 3, 5, 10, 15-, 20-, 30-, and 45-minutes postdose; and at 1, 1.5, 2, 3, 4, 5, 6, 8, 10-, 12-, 16- and 24-hours postdose for plasma salbutamol determination. PK collection will be from the start of study intervention (first inhalation).
- m. **AE and SAE review:** AEs will be collected from the start of study intervention until final follow-up telephone call. SAEs will be collected from the signing of the ICF until final follow-up telephone call.

Table 2 Timing of Assessments

Assessment	Timing of Dosing
Study intervention administration	Dosing for each participant will be around the same time (± 1 hour) at each intervention period day. All postdose timepoints will be from the start of each study intervention i.e., the first inhalation.
PK blood sampling	Predose samples will be obtained between waking up and dosing. Postdose samples up to 30 minutes will be obtained with a time window of ± 1 minute. Thereafter, postdose samples will be obtained with time margins of $\pm 5\%$ of the time that has passed since (last) dosing.
PD blood sampling	For PD blood samples, predose samples will be obtained between waking up and dosing. Postdose samples up to 30 minutes will be obtained with a time window of ± 2 minutes. Thereafter, postdose samples will be obtained with time margins of $\pm 5\%$ of the time that has passed since (last) dosing.
Safety assessments	For safety assessments, predose assessments will be performed between waking up and dosing. For safety assessments up to 2.5 hours postdose, a time window of ± 15 minutes is allowed. Thereafter, serial postdose assessments (e.g., multiple assessments within any given day) will be performed with time margins of $\pm 10\%$ of the time that has passed since (last) dosing.

Note. When assessments are planned for the same scheme time, the order of the assessments should be arranged in such a way that ECG and vital signs will be done first followed by the PK (then PD) blood sampling, with PK blood sampling exactly on time.

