#### 4.4. Exploratory Endpoint(s) Analyses

The exploratory pharmacodynamics (PD) endpoints are -

- Minimum serum potassium
- MHR
- Maximum QTc interval

The exploratory pharmacodynamics (PD) endpoints will be analyzed for Cohort 1 and Cohort 2 using FAS. All PD parameters will be summarized by study treatment.

Statistical model for the analysis of exploratory PD endpoints in each cohort

Following loge-transformation, minimum serum potassium, MHR and maximum QTcF interval will be analyzed using mixed effect model approach with fixed effect for period, treatment group. The point estimates and their associated 90% CI will then be back-transformed to provide point estimates and 90% CI for the ratios (GMR) of HFA-152a MDI (test)/HFA-134a MDI (reference).

For the untransformed data of pharmacodynamics (PD) parameters (minimum serum potassium, MHR (Maximum HR, maximum QTc interval)), descriptive statistics (N, n, AM, 95% CI of AM, SD) median, minimum and maximum) will be computed for FAS.

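### Maximum heart rate and maximum QTcF rest on one postdose ECG per period, so within a period they are 30-minute values, and the five postdose pulse rates are not used for MHR

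*Protocol*

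**What the plan says.** Protocol section 3 (Table 3) and SAP section 1.1 list three exploratory PD endpoints: minimum serum potassium, MHR and maximum QTc. The protocol's abbreviation list expands MHR as "Maximum Heart Rate".

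SAP section 4.4 states that, after log transformation, "minimum serum potassium, MHR and maximum QTcF interval will be analyzed using mixed effect model approach", with fixed effects for period and treatment. Results are back-transformed to test/reference ratios with 90% CIs. Protocol section 9.3.2.1 plans the same comparison, with participants as random effects.

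The source of heart rate and QTc is given in protocol section 1.3, footnote i: "As the ECG parameters QTc and HR will be PD parameters". On each dosing day the ECG is recorded "at predose and at: 30 minutes postdose and at discharge". The predose recording is a triplicate, averaged to give the baseline. After dosing, "Postdose 12-lead ECG measurements will be single measurements on all dosing days". The one exception is that "if an ECG meets potential stopping criteria, then the ECG measurement should be repeated in triplicate".

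Footnote h schedules blood pressure and pulse rate, supine, on each dosing day "at predose and at the following time points postdose: 15, 30 minutes, 1, 2, 4 hours and at discharge". Protocol section 9.3.1.8 and SAP section 4.5.3.2 summarise these descriptively as safety data.

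Neither maximum is defined in the visible text. Protocol section 8.6 lists only potassium parameters under pharmacodynamics, and SAP section 4.4 names the endpoints without a derivation. The SAP version history says the derivation leaves each participant with one PD observation for the whole study, and removes the random effect on that ground.

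**The concern.** A maximum is a summary over several postdose readings. If only one is scheduled, the endpoint is a fixed-time value under another name.

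This matters because protocol section 2.3.1 names a possible higher effective dose from HFA-152a as a risk, and lists pulse-rate changes and QTc prolongation among the class effects. A test/reference ratio near 1 for MHR or maximum QTcF would be read as evidence that peak effects are alike, when the ECG schedule compares the products at 30 minutes only.

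The missing derivation is a second problem. A programmer must decide which readings count and how many values each participant contributes. Different choices give different endpoints.

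**Working it through.** The plan states no power or precision for these endpoints, so there is no figure to reproduce. The check is a count of scheduled readings, followed by a comparison of the sections.

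**1. Scheduled postdose readings on a dosing day** (protocol section 1.3, footnotes g, h and i; discharge excluded)

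| Measure | Postdose times | Per period | Over 4 periods | Per treatment (2 periods) |
|---|---|---|---|---|
| ECG heart rate | 30 min | 1 | 4 × 1 = 4 | 2 |
| ECG QTcF | 30 min | 1 | 4 × 1 = 4 | 2 |
| Supine pulse rate | 15, 30 min; 1, 2, 4 h | 5 | 4 × 5 = 20 | 10 |
| Serum potassium | 15, 30 min; 1, 1.5, 2, 4 h | 6 | 4 × 6 = 24 | 12 |

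The maximum of a single number is that number. Minimum potassium is an extremum over six values per period. MHR and maximum QTcF are the 30-minute reading.

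**2. Which other ECGs could enter a period maximum**

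SAP section 6.2.2 runs each of Periods 1 to 3 from its own dose to the next period's dose. The next period's predose ECG therefore falls inside it. Period 4 runs to one day after its dose. The discharge ECG, about 24 hours after the Day 10 dose, may fall inside or just outside. Without an explicit rule, a period maximum could be a reading taken about one day (Period 4) or three days (Periods 1 to 3) after dosing.

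**3. How many values per participant**

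The sequences are TRRT and RTTR, so each treatment is given in two periods.

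| Reading of the derivation | ECG values behind each maximum | Values per participant | Fit with period and treatment terms |
|---|---|---|---|
| One value for the whole study | 4 (2 test, 2 reference) | 1 | Poor: the maximum is taken across both treatments and all periods |
| One value per treatment | 2 | 2 | Poor: the maximum spans two periods |
| One value per period | 1 | 4 | Good, but the value is the 30-minute reading |

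The SAP version history describes the first row, while the model in SAP section 4.4 needs the third. With four values per participant, the stated reason for removing the random effect no longer applies.

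**4. What can be repaired from scheduled data**

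Heart rate can be: five postdose pulse rates exist in every period. QTcF cannot: with one postdose ECG per period it is a 30-minute value unless more ECGs are scheduled.

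**The case against.** The strongest defence is that a derivation exists, since the SAP version history refers to one, and parts of the SAP's data-derivation appendix are redacted. It may take a maximum across replicate periods. This stands to the extent that only the within-period statement is certain. A maximum across occasions would still not be a peak postdose effect, and it would still fit the model poorly.

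It is also fair that a fixed-time reading in a replicate crossover is a valid comparison of the products at that time. The fault lies in the label and the missing rule.

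Four stronger inferences are tempting, and the documents do not support them.

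- **That the pulse rates are wasted.** They are a named secondary safety endpoint, summarised and listed. They are only not used for MHR.
- **That 30 minutes misses the peak.** No section gives the time of peak heart-rate or QTc effect. Protocol section 2.2 gives onset and duration of bronchodilation only.
- **That peak heart rate is understated by a known number of beats.** The documents give no within-period SD. If five readings share a common mean, their expected maximum exceeds that mean by about 1.16 SD with independent readings, 0.83 SD at correlation 0.5 and 0.52 SD at 0.8 (simulated). Under that assumption there is no peak to miss. The excess is noise that any maximum picks up, it affects both treatments alike, and it is not a bias in the test/reference ratio.
- **That the ECG may be taken anywhere from 15 to 45 minutes.** Protocol Table 2 does say "For safety assessments up to 2.5 hours postdose, a time window of" ±15 minutes. The note below it places ECG and vital signs before the PK sample, which must be exactly on time, and the 30-minute PK sample has a ±1-minute window. That largely rules out the late end, so no change to the window is asked for.

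**Conclusion.** The point holds in a limited form. Heart rate and QTc for PD come from the ECG, with one single scheduled postdose reading per period. Within a period, MHR and maximum QTcF are therefore 30-minute values. The remark that each participant has one PD observation for the study contradicts the period-and-treatment model in SAP section 4.4.

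The size is the count itself: one reading for each ECG endpoint, against five for pulse rate and six for potassium. No numerical bias in either ratio can be derived from the documents, and none is claimed. The conclusion assumes that footnote i is the operative ECG schedule and that no redacted text defines a different source or rule.

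The consequence is confined to exploratory endpoints. The primary PK analysis and the sample size do not depend on it. It is still worth correcting, because a result reported as a ratio of maxima would claim more than was measured.

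**What to change.** In SAP section 4.4, with matching wording in protocol Table 3, footnote i and section 9.3.2.1:

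1. Derive MHR per period as the largest of the five scheduled postdose supine pulse rates (15 and 30 minutes; 1, 2 and 4 hours). Alternatively, keep the ECG value and relabel it ECG heart rate at 30 minutes.
2. Rename maximum QTc as QTcF at 30 minutes postdose.
3. Exclude predose, next-period predose and discharge readings from both.
4. Keep one value per participant per period, and replace the remark about one observation for the study. The model must then allow for four correlated values per participant, as the random participant effect in protocol section 9.3.2.1 does.
5. Adjust each endpoint for its same-period predose value, on the same device. SAP Table 1 already names a predose baseline for each period, but its second footnote mentions only the Day 1 triplicate and should be aligned.

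The cost is SAP text, programming and a matching change to the protocol endpoint wording. No new procedures or samples are needed. The downside is that a pulse-based MHR comes from the vital-signs device instead of the ECG, so it is not interchangeable with an ECG heart rate and should be labelled accordingly.
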